12.1 Protocol Deviations

A table will be produced summarizing, by treatment group, the number and percentage of subjects with a major protocol deviation, overall and by type of deviation (ITT and mITT Analysis Sets).

All protocol deviations will be listed and each will be marked whether it is major or minor. Major clinical deviations who affect efficacy will result in exclusion from the PP Analysis Set.

Major protocol deviations affecting efficacy include: Prohibited medication/procedures during the treatment period and inadequate treatment compliance i.e. deviations from the planned amount of active dose and schedule of treatment (out of allowed window as specified in the "Analysis Sets" document). Subjects who have (actual total dose)/(planned total dose)*100 within 75-100 % will be considered treatment compliant. If subject was randomized to placebo group but instead received at least one dose of sprifermin, then this subject will be classified as having major protocol deviation. Additionally subjects identified in the Note To File: "NTF_QC of primary endpoint MRI FORWARD 17MAY2016", will be excluded from the PP.

13 Demographics and Other Baseline Characteristics

Demographics and other baseline characteristics will be presented descriptively for the analysis sets described in table 2 (Section 10). Moreover, demographics will be presented by country.

By-subject listings accompanying each demographic and baseline characteristics table will be produced.

13.1 Demographics

Demographic variables include age, sex, height, weight, BMI, race, ethnicity, and country.

Medical History

Medical history (other than knee OA) will be summarized descriptively by MedDRA SOC and PT.

13.3 Other Baseline Characteristics

Other Baseline Characteristics include the following variables:

- Alcohol and nicotine consumption
- Specification of target knee OA: (KL Grade 2 or 3, target knee location (Left or Right knee), medial and lateral mJSW, Anatomic axis angle (AAA) of knee alignment [in degrees calculated as 180 ANGLE, where ANGLE is the value corresponding to xmtestcd = 'ANGLE'], response to Question 1 of the WOMAC pain index at screening, and time since diagnosis
- Contralateral knee: KL Grade (0, 1, 2, 3), medial and lateral mJSW

- Pain in other joints (yes/no, and if yes, how many joints and which joints specifically)
- All other attributes defined in subgroups analysis set in Section 10.

14 Previous or Concomitant Medications/Procedures

Medication start and stop dates will be compared to the date of first dose of study medication, see appendix 20.3, to allow medications to be classified as

- (a) Previous,
- (b) Concomitant, or
- (c) Post-treatment medications.

All medications categories will be summarized and listed. Medications that start and stop prior to the date of first dose of study medication will be classified as previous medication. If a medication starts or stops on or after the date of first dose of study medication and prior to last dose, then the medication will be classified as Concomitant. Medications that start after last injection will not be considered concomitant and will be categorized as Post-treatment medications. If medication start and/or stop dates are missing or partial, the dates will be compared with the date of first dose of study medication. Medications will be assumed to be Concomitant, unless there is clear evidence (through comparison of partial dates) to suggest that the medication stopped prior to the first dose of study medication (in which case the medication will be assumed to be Previous medication) or started after last injection (in which case the medication will be assumed to be Post-treatment medication).

Pain and other medication such as NSAIDs taken in each of the three categories (a,b,c) described above will be summarized and listed. List of pain medication is attached in Appendix 19.2.

All medications will be coded using the latest version of the WhoDrug Anatomic therapeutic class (ATC) Medications using the indication or using the secondary level of the ATC code. Coding will be updated for the 5-year analysis.

Procedures will be listed only.

15 Treatment Compliance and Exposure

Exposure to sprifermin will be summarized descriptively in terms of:

- Duration of exposure = date of last injection date of first injection +1
- Total dose (μg)= sum of (number of X μg dose injections * X μg)
- Listing of treatment exposure including time between injections within a cycle and time between last injection of previous cycle and first injection of next cycle will be provided.

Treatment compliance will be summarized descriptively in terms of:

• Mean number of injections by cycle and overall;

- Number of subjects (and percentage) receiving 1,2,3....12 injections; and
- Number of subjects (and percentage) with 75-100 % treatment compliance. Subjects who have (actual total dose)/(planned total dose)*100 within 75-100 % will be considered treatment compliant. Treatment compliance will not be summarized for the placebo group.
- Listing of subjects receiving wrong medication will be provided.

16 Endpoint Evaluation

This section presents specifications for analyzing the trial endpoints specified in the Clinical Trial Protocol to meet the trial objective. Endpoints not identified in the Clinical Trial Protocol are also presented here.

16.1 Primary Efficacy Endpoint Analyses

The primary endpoint for the DBPC treatment phase is the change from baseline in cartilage thickness in the total femorotibial joint as evaluated by quantitative MRI at 2 years in the mITT. Cartilage thickness of the total femorotibial joint will be calculated in two ways:

- 1. Average Cartilage Thickness (Total Volume divided by Total Surface Area): (MFTC.VC+LFTC.VC)/(cMF.tAB+cLF.tAB+MT.tAB+LT.tAB)
- 2. Total Cartilage Thickness (sum of cartilage thickness in medial and lateral compartment): MFTC_ThCtAB_aMe + LFTC_ThCtAB_aMe

These 2 variables are highly correlated, but since the first one (average) was used in the previous study as primary endpoint and power was based on this variable, this will be also the variable to be used as primary endpoint. Of these two (1) is considered the primary, and only this is summarized and analyzed, (2) is just derived in ADaM. Definitions of these variables are provided in the imaging transfer specifications document.

Summary statistics

Summary statistics for change from baseline in cartilage thickness in the total femorotibial joint will be presented both for the DBPC treatment phase and for the follow-up phase.

Summary statistics will be provided per timepoint (including LOCF) for:

- Cartilage thickness in the femorotibial joint as evaluated by quantitative MRI
- absolute change from baseline in cartilage thickness by quantitative MRI
- percentage change from baseline in cartilage thickness by quantitative MRI

Primary analyses of linear dose-relationship and treatment effect

The primary efficacy analyses will consist of testing the linear dose relationship at 2 years and the treatment effect and will be presented for the DBPC treatment phase.

Sprifermin (AS902330) Statistical Analysis Plan (Final) EMR700692 006 – v1.0

The significance level will be set at 5% two-sided.

For the linear dose relationship testing, the null and alternative hypotheses will be conducted using the following linear contrast testing:

```
H0: -2 Mean (Placebo) - 1 Mean (180 mcg) + 0 Mean (360 mcg) + 1 Mean (600 mcg) + 2 Mean (1200 mcg) = 0 H1: -2 Mean (Placebo) - 1 Mean (180 mcg) + 0 Mean (360 mcg) + 1 Mean (600 mcg) + 2 Mean (1200 mcg) \neq 0
```

where the doses shown are the total doses of sprifermin to be administered over the DBPC treatment phase.

The treatment effect on the primary endpoint will be assessed through dose-ranging using a repeated measurement analysis of variance (ANOVA) (using PROC MIXED in SAS) on absolute change from baseline, including the treatment group, the time point, and the (pooled) country as fixed factors and the baseline value as covariate and treatment by time point as interaction, see "ANOVA models" in section 11. Repeated measures over time will be accounted for using an 'unstructured' covariance pattern, and if the model fails to converge 'compound symmetry' will be used.

If the null hypothesis is rejected, the alternative hypothesis will be accepted and it will be concluded that there is a dose relationship versus placebo over time.

The analysis of the primary efficacy endpoint will also consist of testing the overall treatment effect at 2 years and will therefore only be conducted for the DBPC treatment phase.

The significance level will be set at 5% two-sided.

For the overall treatment effect testing, the null and alternative hypotheses will be:

```
H0: Mean (Placebo) = Mean (180 mcg) = Mean (360 mcg) = Mean (600 mcg) = Mean (1200 mcg) H1: Mean (i) \neq Mean (j) for some i \neq j and i, j = Placebo or 180 mcg or 360 mcg or 600 mcg or 1200 mcg.
```

where the doses shown are the total doses of sprifermin to be administered over the DBPC treatment phase.

If the null hypothesis is rejected, the alternative hypothesis will be accepted and it will be concluded that there is at least one group that differs from the other groups.

Pairwise comparisons of absolute change from baseline in cartilage thickness (sprifermin treatment groups versus placebo) will be performed within the context of this modeling framework. For each pairwise comparison, the difference between treatments and the corresponding 95% CI and p-value will be presented. P-values (corresponding to Type 3 tests of fixed effects) will be reported for all covariates in the original 'Overall' model for all time points combined (i.e. baseline value, treatment, timepoint, treatment-by-timepoint interaction, country) and for all timepoints. Estimated coefficients, p-values and 95% CIs will be presented overall and at each timepoint for

(i) the dose relationship (linear trend); and, (ii) each pairwise comparison between dose level and placebo.

A plot of means and 95% CI including all time points (including LOCF) per treatment group for dose relationship will be presented. All treatment groups will be presented in one plot.

The primary efficacy analysis as well as secondary MRI endpoints will be performed on the mITT Analysis Set.

Sensitivity analysis using Per Protocol Analysis Set

In order to assess the robustness of the primary analysis, the test for linear dose-relationship and for the overall treatment effect will be repeated using the Per-Protocol Analysis Set.

Sensitivity analysis regarding fixed effects and covariates in the model

A non-parametric analysis will be conducted for the ordered data of cartilage thickness in the total femorotibial joint as an alternative method for the primary analysis. Data will be ordered by the magnitude of absolute change-from-baseline over 2 years during DBPC treatment phase using rank transformation. This will be done only for the mITT Analysis Set.

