Trial Periods (if applicable)	The screening period will comprise a period of 4 to 42 days during which a subject's eligibility will be determined, beginning at signature of the Informed Consent Form (ICF).
	During the screening visits, eligibility will be assessed and the target knee will be defined. At the baseline visit, eligibility will be confirmed, randomization will occur, and the first IMP injection will be given (Week 0/Visit 2). The last of the four cycles of 3 injections of IMP will begin on Week 78/Visit 17, and the last dose of IMP is scheduled to be administered at Week 80/Visit 19.

Trial visits during the two-year DBPC treatment phase will take place at Weeks 0 (randomization and first IMP injection), 1, 2, 3, 12, 26, 27, 28, 29, 38, 52, 53, 54, 55, 64, 78, 79, 80, 81, 90, and 104.

Major efficacy assessments will take place on the first day of each treatment cycle and then at the end of the DBPC treatment phase (Week 104/Visit 22).

Minor efficacy assessments will take place 9 weeks after each treatment cycle.

Adverse Events (AE) and concomitant medications will be reviewed and vital signs will be measured at all trial visits.

Trial assessments during the 3-year extended follow-up phase will take place at 6-month intervals from Week 104/Visit 22 through Week 260/Visit 28.

Randomization and Blinding

Eligible subjects will be randomized to one of the 5 treatment parallel groups with an allocation ratio of 1:1:1:1:1. Randomization will be stratified by country.

The central randomization service's IVRS will be used to randomize subjects to treatment.

The allocated randomization number will only be used for dosing.

The IVRS will also be used to assign a blinded treatment kit at each subsequent treatment visit.

7 Sample Size/Randomization

As described in protocol Section 8.1: The sample size was determined for the primary endpoint: Change from baseline in cartilage thickness in the total femorotibial joint as evaluated by quantitative MRI at 2 years.

[figure not shown]
This trial is set up to detect a potential dose relationship, based on the total dose of sprifermin received over the 2 years, in limiting the reduction of or increasing the cartilage thickness in the total femorotibial joint, assuming:

- 1. A mean change from baseline at 2 years:
 - -0.03 mm in the placebo group (i.e., 0 mcg over 2 years)
 - -0.01 mm in the sprifermin 30 mcg once a year group (i.e., 180 mcg over 2 years)

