 - +0.01 mm in the sprifermin 30 mcg twice a year group (i.e., 360 mcg over 2 years)
 - +0.01 mm in the sprifermin 100 mcg once a year group (i.e., 600 mcg over 2 years)
 - +0.03 mm in the sprifermin 100 mcg twice a year group (i.e., 1200 mcg over 2 years)
- 2. A common SD (standard deviation) of 0.10 mm
- 3. A type-one error, α , of the primary efficacy analysis set at 5% two-sided
- 4. Normal distribution.

The above assumptions were based on available MRI data from the Osteoarthritis Initiative (OAI) (http://oai.epiucsf.org/datarelease/) and from the Phase I Proof of concept (POC) trial (28980).

Figure 1 Expected Mean Changes in Cartilage Thickness (mm) in Total Knee at 2 Years, SD=0.10

SD: standard deviation

A minor deviation from linearity has been introduced in these hypotheses based on the expectation of similar changes for the sprifermin 30 mcg twice a year, and sprifermin 100 mcg once a year groups. Indeed, according to the current knowledge of the biological mechanism of action of sprifermin, the treatment effect of the highest dose (100 mcg) given once a year could be similar to that of a lower dose (30 mcg) given twice a year. Moreover, the variability of the measure is large, and therefore a deviation from perfect linearity may be expected.

Calculations showed that:

- 55 evaluable subjects in each group (total 275 subjects) will ensure a power of 90% for detecting a linear dose relationship using a linear trend test,
- 76 evaluable subjects in each group (total 380 subjects) will ensure a power of 90% for detecting an overall treatment effect (meaning that at least one group differs from the other groups) as well.

Based on recent literature and other trial experience (see protocol references 45 and 46), the subject discontinuation rate is estimated to be close to 30% at two years. Assuming a 30% drop-out rate, a total of 545 subjects should be randomized (109 subjects per group) in order to detect an overall treatment effect.

In order to be able to demonstrate that structural improvement translates into symptomatic benefit, it is important that the study be adequately powered to detect significant differences in normalized WOMAC scores. With 76 evaluable subjects per treatment group, the power to show a statistically

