8.2 Analysis of data from the follow-up phase

An overview of endpoints and type of analysis for the follow-up phase is provided in Appendix 19.1. In general, the same endpoints (for efficacy and safety) will be presented as for the treatment phase and the analysis of follow-up period (up to week 260) will be integrated combining all available data in the entire 5 years period (including data from the DBPC). No multiplicity adjustment for the integrated analysis will be done, as the efficacy evaluation on the integrated data is considered exploratory.

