ANOVA models are used for several endpoints. For each endpoint all available time-points except LOCF (specified in table 3) should be included and summarized. The general model specification for model that include 4 post-baseline measurements (i.e. qMRI) in SAS will be:

```
proc mixed data=p3 method=reml;
  class grpn vs usubjid CNTRGR1N ;
 model &var. = grpn vs grpn*vs base CNTRGR1N / solution;
  repeated vs / subject=usubjid type=&type. r;
  lsmeans grpn / adjust=dunnett diff=control('1') cl;
  lsmeans grpn*vs / adjust=dunnett diff=control('1' 'Week 26') cl;
  lsmeans grpn*vs / adjust=dunnett diff=control('1' 'Week 52') cl;
  lsmeans grpn*vs / adjust=dunnett diff=control('1' 'Week 78') cl;
 lsmeans grpn*vs / adjust=dunnett diff=control('1' 'Week 104') cl;
  lsmeans grpn*vs / slice=vs;
  contrast 'Linear trend (overall)' grpn -2 -1 0 1 2;
  contrast 'Linear trend at Week 26' grpn -2 -1 0 1 2 grpn*vs -2 0 0 0 -1 0 0
0 0 0 0 0 1 0 0 0 2 0 0 0;
  contrast 'Linear trend at Week 52' grpn -2 -1 0 1 2 grpn*vs 0 -2 0 0 0 -1 0
0 0 0 0 0 0 1 0 0 0 2 0 0;
  contrast 'Linear trend at Week 78' grpn -2 -1 0 1 2 grpn*vs 0 0 -2 0 0 0 -1
0 0 0 0 0 0 0 1 0 0 0 2 0;
  contrast 'Linear trend at Week 104' grpn -2 -1 0 1 2 grpn*vs 0 0 0 -2 0 0 0
-1 0 0 0 0 0 0 0 1 0 0 0 2;
```

run;

12 Disposition of Subjects and Discontinuations

This section presents specifications for reporting subject disposition and treatment/trial discontinuations. Additionally, procedures for reporting protocol deviations are provided.

Subject disposition will be presented for all subjects and by treatment group in terms of:

- Total number of subjects screened (i.e. subjects who signed informed consent)
- Number and percentages of subjects discontinuing the trial prior to randomization divided by main reason for discontinuation (did not meet all eligibility criteria, withdrew consent, other), by country and site, and overall.
- Number and percentages of randomized subjects.
- Number and percentages of exposed subjects
- Number and percentages of randomized subjects who completed the DBPC treatment phase. For the 2-year analysis a completer is a subject with no date of study discontinuation before day 819.
- Number and percentages of randomized subjects who discontinued the trial after randomization, during DPBC i.e. before day 819, and during extended follow up phase (grouped by treatment) and main reason (AE, death, lost to follow-up, etc).

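### If the unstructured model does not converge, the SAP goes straight to homogeneous compound symmetry, so the Week 104 standard error is wrong whenever the variance of change differs between visits

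*SAP*

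**What the plan says.** SAP 16.1 analyses change in total femorotibial cartilage thickness with a repeated-measures model and an unstructured covariance over visits. Its only contingency is that "if the model fails to converge 'compound symmetry' will be used".

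The code is printed in SAP section 11 under ANOVA models: "proc mixed data=p3 method=reml" and "repeated vs / subject=usubjid type=&type. r". A macro variable sets one covariance type for all visits. There is no EMPIRICAL option, so standard errors are model-based. The code is introduced thus: "The general model specification for model that include 4 post-baseline measurements (i.e. qMRI) in SAS will be". The Week 104 trend contrast (weights -2, -1, 0, 1, 2) and the comparisons with placebo come from this one fit. On error control, SAP 16.1 states: "The significance level will be set at 5% two-sided".

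SAP 16.2 reuses a similar model for regional thickness, cartilage volume, minimum joint space width, WOMAC total and sub scores, and the 20-meter walk test. For the extended follow-up, SAP 8.2 says that "the analysis of follow-up period (up to week 260) will be integrated combining all available data in the entire 5 years period".

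The only variability figure for the MRI endpoint is in SAP section 7 (and protocol 8.1), for change at 2 years: "A common SD (standard deviation) of 0.10 mm". No SD is given for Weeks 26, 52 or 78.

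**The concern.** Compound symmetry assumes one variance at every visit and one correlation between every pair of visits. The primary tests are read at Week 104. After the fallback, their standard error would come from a variance pooled over all four visits, not from the variance at Week 104. If earlier changes are less variable, the 2-year standard error is understated, the trend and overall tests reject too often, and the confidence intervals are too narrow. If earlier changes are more variable, the reverse holds. In either case the stated 5% level is not assured once the fallback is used, and whether it is used depends on whether the software converges.

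Nothing else in the plan corrects this. The per-protocol and rank-transformed sensitivity analyses name no other covariance structure. The unequal-variance rule in SAP section 11 concerns differences between treatment groups, not between visits. The model check listed in SAP Appendix 19.1 has no stated content.

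**Working it through.** **The plan's own figures.** Inputs are the assumed means in SAP section 7 (-0.03, -0.01, +0.01, +0.01, +0.03 mm), SD 0.10 mm and two-sided 5%.
- Trend: the contrast is 0.06 + 0.01 + 0 + 0.01 + 0.06 = 0.14. Its SE at 55 per group is 0.10 × √(10/55) = 0.0426. The noncentrality is 3.28 and power is 90.5% (stated: 90%).
- Overall test: the squared deviations of the means sum to 0.00208. The noncentrality at 76 per group is 76 × 0.00208/0.01 = 15.8 and power is 90.4% (stated: 90%).
- Dropout: 76/0.7 = 108.6, so 109 per group and 545 in total, as stated.

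The sample size is therefore not in question. The point concerns the analysis only.

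**Effect of the fallback with complete data.** The fitted compound-symmetry variance is the mean of the four visit variances, so

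r = reported SE / true SE at Week 104 = √(mean visit variance / Week 104 variance).

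In large samples the actual error is 2[1 - Φ(1.96 r)] for the trend test and P(χ² on 4 df > 9.49 r²) for the overall test.

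The Week 104 SD is fixed at 0.10 mm, except that all earlier SDs are assumptions. Worked line for 0.07 rising to 0.10: mean variance = (0.0049 + 0.0064 + 0.0081 + 0.0100)/4 = 0.00735; r = √0.735 = 0.857; 1.96 × 0.857 = 1.68; error 9.3%.

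| Assumed SD (mm), Weeks 26/52/78/104 | Mean variance | r | Trend test | Overall test |
|---|---|---|---|---|
| 0.10 throughout | 0.01000 | 1.00 | 5.0% | 5.0% |
| 0.085/0.090/0.095/0.100 | 0.00859 | 0.93 | 6.9% | 8.6% |
| 0.070/0.080/0.090/0.100 | 0.00735 | 0.86 | 9.3% | 13.7% |
| 0.050/0.071/0.087/0.100 (variance proportional to time) | 0.00625 | 0.79 | 12.1% | 20.5% |
| 0.120/0.113/0.106/0.100 (falling) | 0.01210 | 1.10 | 3.1% | 2.2% |

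**With the plan's 30% dropout**, taken as completely random and steady over visits, r becomes 0.92, 0.84 and 0.75 to 0.76 in the three growth rows. Trend-test error is then 7.2%, 10.0% and 13.5% to 14.0%. In the falling row r is 1.11 and the error 3.0%.

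In standard errors, take 0.07 rising to 0.10, correlation 0.6 and 109 per group. Compound symmetry reports a pairwise SE of 0.0953 × √(2/109) = 0.0129 mm, against a true 0.1134 × √(2/109) = 0.0154 mm.

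**A smaller, separate effect.** With constant SD, a decaying correlation (0.7 between adjacent visits) and the same dropout, r is 0.97 and the trend-test error 5.7%. This comes from the common correlation, not the common variance.

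**Where the fallback might be used.** An unstructured matrix over k visits has k(k+1)/2 parameters. From SAP Table 3:
- MRI to Week 104: k = 4, 10 parameters.
- WOMAC and walk test to Week 104: k = 8, 36 parameters.
- Over 5 years: k = 14 (105 parameters) for questionnaires and k = 7 (28) for MRI.

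**The case against.** Harm needs two things to happen together: the unstructured fit must fail, and the variance must differ between visits. For the primary model, with 10 parameters and about 545 subjects, failure is unlikely. Where failure is more plausible, as for WOMAC and the walk test, no SD pattern is available and no error rate has been computed. This stands, and it limits the practical weight of the point.

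Growth of SD over time is nowhere in the documents. The 12.1% case has variance proportional to time, which leaves no room for constant reading error in a difference of two MRI measurements. If, as an assumption, 75% of the Week 104 variance were constant and 25% grew linearly, the mean variance would be 0.75 + 0.25 × 0.625 = 0.906 of the Week 104 value. Then r = 0.95 and the error is about 6.2%. A reader might infer that the primary test is anti-conservative as planned. The documents do not support that: the unstructured model comes first, and the direction after fallback depends on an unknown SD pattern.

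A reader might also infer from SAP 8.2 that a 14-visit, 105-parameter model will be fitted. That is unclear. The footnote to SAP Table 2 limits the follow-up analysis set to summary statistics, while Appendix 19.1 lists an analysis in follow-up for several endpoints. SAP 8.2 calls the integrated efficacy evaluation exploratory.

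Finally, SDs are tabulated by visit, so a discrepancy could be seen, and this is a Phase II trial that advises caution with p-values. Both are true, but neither corrects the standard error.

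**Conclusion.** The point holds as a conditional one. If the fallback is used and the variance of change differs between visits, the reported Week 104 standard error is wrong, in a direction set by how the SD moves over time. On assumed SD patterns ending at 0.10 mm, the complete-data trend-test error runs from about 3% (falling SD) through 5.0% (constant) and about 7% to 9% (modest growth) to 12.1% in the strong case. The overall test moves further in each direction. These are large-sample figures, and only the 2-year SD comes from the documents.

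The risk to the primary MRI analysis is low because that model should converge. The risk is more realistic for the 2-year WOMAC and walk-test models. The change is worth making because a contingency rule should be valid when it is needed, and this one is easily repaired.

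**What to change.** Replace the fallback in SAP 16.1 with a structure that keeps visit-specific variances. Heterogeneous compound symmetry (CSH) is enough for the main problem. Heterogeneous Toeplitz may be tried before it for the 2-year visits, which are roughly equally spaced (26 weeks for MRI; 12 to 14 weeks for questionnaires), and it also relaxes the common correlation. It indexes correlation by visit order, so it does not suit data that run past Week 104, where the spacing changes. Allow homogeneous compound symmetry only with the EMPIRICAL (sandwich) option. State that the rule applies to every endpoint that uses the section 11 model, and settle it before unblinding. If a 5-year repeated-measures model is intended, reconcile the Table 2 footnote with Appendix 19.1.

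Where the fallback structure describes the data, or sandwich errors are used, r returns to 1.00 and both tests to about 5% in large samples. The cost is one SAP sentence and a macro option. No new data are needed, and the unstructured analysis is unchanged when it converges.
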